4. OBJECTIVES*

We propose to prospectively randomize orthopedists, with their patients, to receive (or not) a real-time, web-based system intervention: the OA Care plan. The OA Care plan will include individualized, patient-centric information: (1) trended patient-reported OA pain and function, (2) tailored estimates of likely TJR benefits and risks based on a contemporary US cohort of 25,000 TJR patients (FORCE-TJR Registry), (3) evidence-based information for non-operative care, and (4) individual patient goals.

Specific Aims include:

Aim 1. Patients and their Caregivers/Trusted Others will refine the design, content, and usability of a real-time, web-based individual OA Care plan to guide TJR and non-operative OA care decisions.

Aim 2. Randomize 40 orthopedists, and their patients, to receive the OA Care plan at the time of orthopedic consultation (intervention) vs. usual care (control) and compare (a) OA care decision process and quality and (b) quality of OA care as measured by pain relief and functional gain in the two arms at 6 and 12 months after the decision, and assess the impact of decision quality on quality of OA care.

Aim 3. Randomize 36-40 orthopedists, and their patients, to receive the OA Care plan plus peer, family, and primary care physician support (OA Care plan+Support; intervention called A.S.K. Coaching) vs. the OA Care plan alone and compare the quality of OA care decision and quality of care (pain relief, functional gain) in the two arms.

When moving the PCORI contract to Northwestern in early 2019, we revised the sample size estimates required to meet the same study power and analytic plan for both Aim 2 and Aim 3. Using the early study data, we determined that n=3000 patients in Aim 2 and n=3000 patients in Aim 3 was adequate to meet statistical goals. We also determined that fewer surgeons (N= 36-40) would be required in Aim 3 to consent 3000 patients. PCORI agreed to the changes in number of surgeons and patients. We clarified this change in the ISP.

Based on the components of the Chronic Care Model, this technology-delivered, individualized OA Care plan will enable patients and clinicians to make treatment decisions based on patient symptoms, goals, and comparative effectiveness evidence. We hypothesize that OA Care plan users, as compared to usual care, will report greater decision quality for both TJR or non-

INVESTIGATOR STUDY PLAN

12.14.2021

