7. STUDY-WIDE NUMBER OF SUBJECTS*

Aim 1 Patient Interviews= 30 participants

Caregiver/Trusted Other Interviews = 30 participants

Aims 2 and 3 6000 patients total, 3000 in Aim 2 and 3000 in Aim 3

20-30 surgeon offices will have 1-2 surgeons for each office (total 40 surgeons) contribute 100 consecutive new patients to the study for Aim 2 and an additional 100 patients for Aim 3.

For surgeon qualitative interviews: up to 35 MD surgeons. MD surgeons are not subjects in the ASK study (patients are).

For Aim 3 patient qualitative interviews: Up to 50 patients, with an approximately even breakdown from each of the following groups

- Participated in A.S.K. Coaching + self-reported (on 1-month survey) surgery planned and use of OA Care plan with MD.
- Participated in A.S.K. Coaching + self-reported (on 1-month survey) non-surgical treatment planned and use of OA Care plan with MD.
- Participated in A.S.K. Coaching + self-reported (on 1-month survey) surgery planned and no use of OA Care plan with MD.
- Participated in A.S.K. Coaching + self-reported (on 1-month survey) non-surgical treatment planned and no use of OA Care plan with MD.
- Usual Care arm + self-reported (on 1-month survey) surgery planned and use of OA Care plan with MD.
- Usual Care arm + self-reported (on 1-month survey) non-surgical treatment planned and use of OA Care plan with MD.

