11. PROCEDURES INVOLVED*

See #8 above

Surgeon offices will be randomized to Usual Care or Intervention sites. During Aim 2, after completing the surveys in the clinic, usual care patients and surgeons will have the ability to

INVESTIGATOR STUDY PLAN

12.14.2021

see PRO scores, but will NOT receive feedback (no OA Care Plan) as PROs are the current standard of care in orthopedic clinics. For intervention sites, the patient and surgeon will receive the OA Care Plan (now called A.S.K. report). In Aim 3 (see details above), all patients (both study arms) will receive the A.S.K. report. In addition, patients at intervention sites will be invited to attend the ASK Coaching session to review the content of the report, discuss how to use the report in communication with the medical team, and to learn more about arthritis self-care.

Data collected include the following: New Patient Baseline [Knee/Hip] surveys; 1-month Decisional Conflict Scale;), 6-month and 12-month [Knee/Hip] surveys attached). These data collection sheets will be submitted to the IRB once they are developed.

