12. DATA AND SPECIMEN BANKING*

No specimens will be banked for future use. See #13, Data Management, for data retention and access.

13. Data Analysis and Management*

Responsibility for 6 month and 12 month outcome data collection was transferred from UMMS to Northwestern during 2021. At the completion of study enrollment (on or about March 1, 2022), the UMMS data enrollment and collection services will be completed. At that date, the UMMS data center will have already, or will then, transfer all enrollment, patient-reported, and study data to Northwestern for the analytic team to manage and analyze. The UMMS data center will confirm that they expunged all ASK study data from the web-based data capture systems (DatStat, RedCap) and UMMS data storage files within UMMS.

Aim 1

We will transcribe recorded interviews and code using content analysis techniques to identify themes. We expect to achieve data saturation at or before completing 30 interviews with patients and 30 with caregivers.

AIM 2 and 3. Sample size and effect size estimates:

The trial is designed with $\geq 80\%$ statistical power at 5% significance level to detect intervention effects that are meaningful to both patients and surgeons, and health systems. In total, 40 (Aim 2) or 54 (Aim 3) surgeons will be randomized equally to treatment and control arms with an average of 100 patients/surgeon. Based on data from FORCE-TJR, the intraclass correlation within surgeon is approximately 0.02. Using two independent group t-tests adjusting for within surgeon clustering, the trial can detect an intervention effect of (a) improved decision quality of >0.16 SD ; (b) improved quality of OA care defined in two ways: 6 month post-decision pain relief (KOOS/HOOS) of ≥ 3.3 points for TKR patients (34.1 vs. 37.4; SD=20.8) and ≥ 3.3 for THR patients (45.7 vs. 49.0; SD=20.9) or greater proportion of patients with meaningful pain relief (17 points in HOOS/KOOS pain score) of $\geq 6.1\%$ more TKR patients (77.9% vs. 84.0%) and $\geq 4.2\%$ more THR patients (90% vs. 94.2%).

Aims 2 and 3: Overview of analytic approach. We hypothesize (Aim 2) that patient/clinician use of the OA Careplan will improve decision quality as well as

INVESTIGATOR STUDY PLAN

12.14.2021

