satisfaction with the OA care decision, as compared to usual care. Further, we hypothesize that improved decision quality will mediate quality of OA care as measured by lower pain and higher function at 6 and 12 months (KOOS/HOOS) after decision for both TJR and non-operative care. In Aim 3, we hypothesize that the OA Careplan+Support (vs. OA Careplan alone) will incrementally enhance decision quality and quality of OA care (for those who choose to use the Support) with the same measures used in Aim 2.

The general analytic approaches for Aims 2 and 3 are similar and summarized here. The underlying models extend our previous award-winning TKR outcome prediction model where discrete outcome sub-groups were identified. We will adhere to the intent-to-treat principle to analyze the trial data; the intervention status of the surgeon/site and their patients will be analyzed according to their status at the time of intervention. First, descriptive statistics for all relevant outcomes will be tabulated by treatment arm. Select patient factors (e.g., race, sex, function; comorbid factors) that may contribute to heterogeneity of treatment effects will be compared using univariate methods such as t-test for normally distributed variables, Wilcoxon rank sum test for skewed continuous variables, or Chi² test for categorical variables. We will examine distributions of outcomes, identify proper distribution assumptions, and determine whether or what types of transformations are indicated.

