Because the trial data are hierarchical in nature (repeated measures of the same patient nested within participating surgeons/sites), we will use hierarchical generalized linear latent and mixed models (GLLAMM) to analyze the trial data. The model will consider information at the patient and surgeon levels. The basic unit of analysis is at the patient level. Patients nested within the surgeon/site will be considered exchangeable, and sites/surgeons are considered independent from each other. To account for potential imbalance in site/surgeon and patient characteristics, we will adjust for surgeon/site and patient factors in the regression models. Candidate patient level covariates include joint pain severity, pre-decision physical function level, and comorbid conditions, such as diabetes, renal disease, pulmonary disease, depression, obesity, or congestive health failure. Candidate surgeon variables for adjustment include annual surgical volume, procedure type, or geographic region of US. We will follow the parsimonious principle to derive the final models for evaluating intervention effects. First, we will use GLLAMM models to analyze the association of each plausible patient-and site/surgeon-level factor with the outcomes (quality of decision, change in pain severity, function). Those statistically significant variables ($p < 0.10$) will be included in a subsequent analysis using multivariable models to identify a parsimonious set of independent patient-and site/surgeon-level covariates. Model development will be guided by clinicians and patient advisors to assure that clinically important variables are included. To identify independent site/surgeon-level variables, we will include each of the significant variables separately while forcing the patient-level covariates into the models. The significance of each site/surgeon-level variable will be determined using (partial) likelihood ratio tests. We will identify a subset of site/surgeon indicators that contribute to outcomes ($p < 0.10$), independent of individual-level factors. Furthermore, this subset of significant indicators

INVESTIGATOR STUDY PLAN

12.14.2021

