Aim 3: To evaluate the effect of the OA Careplan+Support (Coaching) on (a) decision quality and (b) pre-to-post decision pain relief and functional gain, we will do the following. The 20 surgeons (and their patients) who received usual care in Aim 2 will receive the OA Careplan intervention (n=2,000) in Aim 3. The 20 surgeons who received the OA Careplan in Aim 2 will now receive the OA Careplan+Support (n=2,000 new patients) in Aim 3. Additional surgeons will be recruited and randomized to the 2 arms. First, we will compare patient characteristics between users and non-users of the SUPPORT. We will then identify patient as well as site/surgeon determinants of the use of the SUPPORT using multi-level logistic regression models, and estimate individual patient's probability (propensity) for any use of SUPPORT strategies. Because use of the SUPPORT is not randomized, we will use inverse propensity weighting approach to estimate the effects of the SUPPORT on outcomes (decision quality, pain, function).

We will begin with descriptive analysis, and estimation of crude OA Careplan+Support intervention effects, overall and by select patient subgroups. We will further use GLLAMM to estimate covariate---adjusted intervention effects, overall and by patient

INVESTIGATOR STUDY PLAN

12.14.2021

subgroup, and adjust for propensity scores, plausible surgeon and patient factors. Statistically significant differences between the two arms indicate possible incremental SUPPORT intervention effect beyond the OA Careplan alone. We will conduct pre-post comparisons of the outcomes (decision quality, pain relief) for patients of the 20 surgeons who were in the OA Careplan intervention arm in Aim 2 and are now in the OA Careplan+Support arm.

Statistically significant pre-post changes in outcomes support possible incremental effects of the SUPPORT intervention. We will derive a usage score of the SUPPORT system (e.g., frequency and duration of use) as an indicator of “dosage” of use and use it to estimate a possible “dose-response” relationship between level of use and patient outcomes in the GLLAMM. We will also identify relevant patient-and site/surgeon predictors of any and higher levels of usage.

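### Patient factors are to be compared with ordinary t, Wilcoxon and chi-square tests although surgeons or offices are allocated; if these are between-arm tests and the plan's ICC of 0.02 applies, about 21-26% of null comparisons would be falsely significant

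*Combined protocol and SAP*

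**What the plan says.** All of this is in Section 13 unless another section is named.

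- **Tests planned.** After a sentence on tabulating outcomes by treatment arm, the overview turns to "Select patient factors (e.g., race, sex, function; comorbid factors) that may contribute to heterogeneity of treatment effects". These "will be compared using univariate methods such as t-test for normally distributed variables, Wilcoxon rank sum test for skewed continuous variables", with chi-square for categorical variables. No allowance for surgeon or office is stated.
- **Unit allocated.** The plan gives two versions. Section 4, Aim 2: "Randomize 40 orthopedists, and their patients, to receive the OA Care plan at the time of orthopedic consultation". Section 11, and Section 8 in the same terms: "Surgeon offices will be randomized to Usual Care or Intervention sites". Section 7 expects 20-30 offices with one or two surgeons each, 40 surgeons in total.
- **Clustering.** The sample-size paragraph states that "the intraclass correlation within surgeon is approximately 0.02", assumes an average of 100 patients per surgeon, and allows for clustering. Section 4 revises the number of patients to 3000 per aim.
- **Outcome models.** The overview recognises that patients are nested in surgeons or sites and specifies hierarchical models (GLLAMM). It adjusts "To account for potential imbalance in site/surgeon and patient characteristics", but chooses covariates by their association with outcomes in GLLAMM at p<0.10, followed by multivariable models with clinical input.
- **Crude effects.** The Aim 3 paragraph lists "estimation of crude OA Careplan+Support intervention effects, overall and by select patient subgroups" before the covariate-adjusted models and names no method for them.

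**The concern.** Every patient of an allocated surgeon or office is in the same arm. A test that counts patients as independent therefore understates the sampling error of a difference between arms. The plan accepts this for outcomes, in both the sample size and the models, but the tests named for patient factors make no such allowance.

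The comparability of the arms carries more weight here than in an individually randomised trial. Under Section 8, patients give verbal consent by telephone to research staff after their surgeon or office has been allocated. In Aim 3 the recruitment packet differs by arm, because patients of Enhanced-arm surgeons also receive the coaching fact sheet and flyer. A reader will look at the baseline comparison for signs of differential recruitment. If ordinary tests flag many differences that are only chance variation between surgeons, that comparison cannot do its job.

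**Working it through.** **Inputs**
- ICC 0.02, 100 patients per surgeon, 20 surgeons per arm in Aim 2, 5% significance level: Section 13. Two-sided testing is assumed, as sidedness is not stated.
- 3000 patients per aim: Section 4. This gives 3000/40 = 75 per surgeon, or 3000/36 = 83 at the lower Aim 3 surgeon count.
- 20-30 offices: Section 7. This gives 3000/30 = 100 to 3000/20 = 150 patients per office.
- The ICC of patient factors is not given. Using 0.02 for race, sex, function or comorbidity is an assumption, so a range is shown.

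**Step 1: reproduce the plan's own figure.** The design effect is DE = 1 + (m-1) x ICC = 1 + 99 x 0.02 = 2.98. The effective number per arm is 2000/2.98 = 671. The detectable difference at 80% power is (1.960 + 0.842) x sqrt(2/671) = 0.153 SD, or 0.157 SD using t with 38 degrees of freedom. The plan states 0.16 SD, so its sample size does use this ICC and cluster size.

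**Step 2: error rate of an ordinary test.** With no true difference between arms, the ordinary statistic has a standard deviation of about sqrt(DE) instead of 1. The true error rate of a nominal two-sided 5% test is 2 x [1 - Phi(1.96/sqrt(DE))].
- 75 per surgeon: DE = 1 + 74 x 0.02 = 2.48; 1.96/1.575 = 1.245; rate 21.3%.
- 83 per surgeon: DE = 2.65; rate 22.8%.
- 100 per surgeon: DE = 2.98; 1.96/1.726 = 1.135; rate 25.6%.

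To hold 5%, an ordinary z would have to exceed 1.96 x 1.575 = 3.09 (75 per surgeon) or 1.96 x 1.726 = 3.38 (100 per surgeon).

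**Step 3: simulation under the null.** There were 20 clusters per arm and ICC 0.02, with 4000 runs (2000 for the rank-sum test).

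| Patients per surgeon | Formula | t | Rank-sum | Chi-square |
|---|---|---|---|---|
| 75 | 21.3% | 22.1% | 20.9% | 21.3% |
| 100 | 25.6% | 27.1% | 27.0% | 25.6% |

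The largest gap, 27.1% against 25.6%, is about two simulation standard errors (sqrt(0.256 x 0.744/4000) = 0.7 percentage points). With an assumed coefficient of variation of 0.5 in cluster size at a mean of 75, the simulated rates are about 25%.

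**Step 4: other ICCs (assumed).**

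| ICC | 75 per surgeon | 100 per surgeon |
|---|---|---|
| 0.005 | 9.4% | 10.9% |
| 0.01 | 13.7% | 16.5% |
| 0.02 | 21.3% | 25.6% |
| 0.05 | 36.6% | 42.2% |

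**Step 5: offices as clusters, 3000 patients, ICC again assumed to be 0.02.**
- 30 offices of 100: DE 2.98, rate 25.6%.
- 25 offices of 120: DE 3.38, rate 28.6%.
- 20 offices of 150: DE 3.98, rate 32.6%.

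**The case against.** The case against has four parts.

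1. **The groups are inferred.** The sentence does not say which groups are compared, and the one before it concerns outcomes. It could mean comparisons across subgroups. The Aim 3 paragraph separately compares users with non-users of the support, a contrast that varies within surgeons, and the design-effect formula does not give its error rate. This stands as a limit: the figures above apply only to comparisons between arms.
2. **The ICC is borrowed.** The value 0.02 appears in a calculation for outcomes. The documents do not show that case mix clusters more than outcomes do, or less. This also stands, and is why the result is given as a range.
3. **The step is descriptive, and other evidence exists.** The tests are preliminary and introduced as examples. Section 8 also keeps age, gender and baseline pain and function for many patients who opt out, decline or are ineligible, so as to study selection. At sites without a business associate agreement, however, an opt-out at the survey closes it and nothing is shared. The objection limits the consequence, but it does not make the named tests valid.
4. **The trial's main inference is protected.** This is correct. A reader might infer that false imbalances would decide which covariates enter the adjusted models. The text does not support that: it gives imbalance as the reason to adjust, but selects covariates by association with outcomes in GLLAMM. A reader might also infer that the crude Aim 3 effects will have intervals that are too narrow. The plan names no method for them, and crude there contrasts with covariate-adjusted, so only a clarification is warranted.

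**Conclusion.** The point holds for the patient-factor comparisons and no further. Read as between-arm tests, the named methods do not fit an allocation by surgeon or office. The false-positive rate is about 21% at 75 patients per surgeon and 26% at 100 if the plan's only ICC applies to these factors, and 26-33% if 20-30 offices are the clusters with the same ICC. Over assumed ICCs of 0.005 to 0.05 it is about 9-42% at 75-100 per surgeon, above 5% throughout. The rate is per comparison with no true difference.

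What suffers is the reported comparability of the arms. The adjusted intervention effects and the covariate screening use GLLAMM and are not affected, and the sample size already allows for clustering. It would be wrong to conclude from this point that the primary analysis is invalid.

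**What to change.** In the overview of the analytic approach in Section 13, replace the sentence on univariate tests with wording to this effect: patient factors will be described by arm with means or percentages and standardised differences, and imbalance will be judged by the size of the difference. Any between-arm p-value will come from a model with the allocated unit as a random effect, or from a test on the means of that unit.

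Name that unit. Sections 4 and 13 say surgeon, and Sections 8 and 11 say office. The analysis must use whichever was actually allocated, because a test on surgeon means would still ignore clustering if offices were allocated.

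In the Aim 3 paragraph, state that the crude arm effects come from the same clustered model without covariates.

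The cost is a change of wording and fewer baseline p-values to report. No further data or patients are needed.

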will be entered into the same model in order to assess their contributions to the outcome under analysis, after adjusting for each other, as well as the patient-level covariates. Model assumptions will be carefully examined. In these model-building processes, effect modifications will be examined by including interaction terms between relevant covariates, and to ensure the heterogeneity of the intervention effects among patient subgroups are adequately considered. The analyses will be conducted with all patients; and then for TKR and THR patients separately. While the primary goal is to understand patient-level covariates with outcomes, it is critical to assess surgeon/site factors that may influence outcome for all, or sub-groups of patients. For example, obese, diabetic patients with cardiac disease may have more positive decision quality and pain relief with a more experienced high-volume surgeon.

Aim 2: To assess the effect of OA Careplan on (a) decision quality and (b) pre-to- post decision pain relief and functional gain, we will do the following. We expect 20 surgeons and 2000 patients will receive the OA Careplan intervention, and another 20 surgeons and 2000 patients will receive usual care. The analyses will be conducted with all patients; and then for TKR and THR patients separately. First, we will tabulate the decision quality and care outcomes by arm and for select patient subgroups (e.g., sex, age, race/ethnicity). Second, we will use GLLAMM to estimate adjusted Careplan intervention effects by including in the models a Careplan indicator (Careplan intervention=1 vs. usual care=0) and a set of site/surgeon and patient variables for adjustment. A statistically significant coefficient of the Careplan indicator signals possible intervention effect. In this analysis, interaction terms between the Careplan indicator and surgeon or patient factors will be examined, statistically significant interaction terms may suggest the existence of heterogeneity in intervention effects. If present, intervention effects will be analyzed and presented by subgroups.

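### No small-sample variance estimator, reference distribution or degrees of freedom is specified for the surgeon-level arm coefficient; if it is tested by maximum likelihood against z, the nominal 5% level is about 6.5% at 36-40 surgeons

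*Combined protocol and SAP*

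**What the plan says.** **Sizing.** The sample-size paragraph of section 13 (Data Analysis and Management) claims at least 80% "statistical power at 5% significance level". The method given is "Using two independent group t-tests adjusting for within surgeon clustering", with an intraclass correlation of about 0.02 and an average of 100 patients per surgeon. On cluster numbers it says "In total, 40 (Aim 2) or 54 (Aim 3) surgeons will be randomized equally to treatment and control arms". Section 4 (Objectives) says instead that "fewer surgeons (N= 36-40) would be required in Aim 3 to consent 3000 patients".

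**Analysis.** The overview of the analytic approach in section 13 states that "we will use hierarchical generalized linear latent and mixed models (GLLAMM) to analyze the trial data". The Aim 2 paragraph gives the decision rule: "A statistically significant coefficient of the Careplan indicator signals possible intervention effect". The Aim 3 paragraph uses the same model and speaks of statistically significant differences between the arms.

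**Covariates.** Candidate surgeon-level variables are annual volume, procedure type and US region. They are screened at p < 0.10, and their significance "will be determined using (partial) likelihood ratio tests". That sentence concerns the choice of site and surgeon covariates, not the arm.

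**What is absent.** Nothing in section 13 names maximum likelihood or REML, a normal or t reference, denominator degrees of freedom, or any permutation or cluster-level test for the arm effect.

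**The concern.** All patients of a surgeon are in the same arm of a given aim, so the precision of the arm comparison is limited by the number of surgeons rather than the number of patients. With K surgeons and q surgeon-level covariate parameters, the test has about K - 2 - q degrees of freedom. A t-test, such as the one used for sizing, allows for this.

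A mixed model fitted by maximum likelihood with a normal reference does not, for two reasons. In the balanced case it divides the between-surgeon sum of squares by K instead of K - 2 - q, so the standard error is too small. It then applies 1.96 instead of the larger t cut-off. Each surgeon-level covariate makes the first error worse.

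At stake is whether the 5% level claimed at the design stage holds for the parallel arm comparisons of decision quality, pain and function, and whether their confidence intervals are wide enough.

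**Working it through.** **Inputs from the documents.** Alpha 0.05 (sidedness not stated; two-sided assumed); intraclass correlation 0.02; 40 surgeons with 100 patients each (section 13); 36-40 surgeons for Aim 3 (section 4) or 54 (section 13); 3,000 patients per aim (sections 4 and 7). The number of surgeon-level parameters finally kept is not fixed, so q = 0, 2 and 5 are shown. Five would be, for example, volume, procedure type and three region terms.

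**Step 1: reproduce the plan's figure.** Design effect = 1 + 99 × 0.02 = 2.98. Effective n per arm = 2000 / 2.98 = 671. Standard error in SD units = √(2/671) = 0.0546. Detectable effect at 80% power on t with 38 df = (2.024 + 0.851) × 0.0546 = 0.157 SD, against the stated 0.16. For pain, 0.157 × 20.8 = 3.27 points and 0.157 × 20.9 = 3.28 points, against the stated 3.3. The plan's figures reproduce with a t reference.

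**Step 2: type I error of the arm coefficient.** For balanced clusters and a normal outcome, with df = K - 2 - q:

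- ML with z: size = P(|t_df| > 1.96 × √(df/K)).
- REML with z: size = P(|t_df| > 1.96).
- REML with t on df: 5.0%, exact in this case.

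Worked example, K = 40 and q = 0: df = 38; 1.96 × √(38/40) = 1.910; P(|t_38| > 1.910) = 6.4%.

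| Surgeons | q | df | ML with z | REML with z |
|---|---|---|---|---|
| 40 | 0 | 38 | 6.4% | 5.7% |
| 40 | 2 | 36 | 7.1% | 5.8% |
| 40 | 5 | 33 | 8.4% | 5.9% |
| 36 | 0 | 34 | 6.5% | 5.8% |
| 36 | 2 | 32 | 7.4% | 5.9% |
| 36 | 5 | 29 | 8.9% | 6.0% |
| 54 | 0 | 52 | 6.0% | 5.5% |
| 54 | 5 | 47 | 7.4% | 5.6% |

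**Step 3: check by simulation.** A random-intercept normal model was fitted by full maximum likelihood, with 4,000 runs per setting (Monte Carlo standard error about 0.4 points), intraclass correlation 0.02, and cluster-size coefficient of variation 0 or 0.6. At 36-40 surgeons, the z-test rejected in 5.7-6.8% of runs with q = 0 and 8.1-9.8% with q = 5. Keeping the ML standard error and changing only the reference to t gave 5.1-6.0% and 7.1-8.6%. Both the variance estimator and the reference therefore need to be specified.

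**Step 4: width of the intervals.** Correct width relative to ML with z = t_(0.975, df) × √(K/df) / 1.96.

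- K = 40, q = 0: 2.024 × 1.026 / 1.96 = 1.06.
- K = 36, q = 2: 2.037 × 1.061 / 1.96 = 1.10.
- K = 36, q = 5: 2.045 × 1.114 / 1.96 = 1.16.

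**The case against.** The strongest reply is that the plan is silent rather than wrong. Section 13 never says maximum likelihood or z for the arm, so a statistician could fit the model by REML with a t reference and contradict nothing in it. This stands, and it makes the figures conditional. The condition is still the natural reading: the named method is a likelihood-based latent-variable model, and likelihood-ratio comparison of models with different fixed effects calls for maximum likelihood. REML with z would still be slightly above 5%.

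Three stronger readings are tempting, and the documents do not support them.

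- A reader might infer that the arm itself is judged by likelihood-ratio tests. Those tests are specified only for choosing surgeon and site covariates. The arm rule is the significant coefficient in the Aim 2 paragraph.
- A reader might take 8-9% as the expected error. That needs about five surgeon-level parameters kept. The plan screens candidates at p < 0.10 and seeks a parsimonious set. In 40,000 simulated balanced trials with that screening and covariates unrelated to outcome, about 0.6 parameters survived on average, and ML-with-z error was 6.8% (36 surgeons), 6.5% (40) and 6.1% (54). Prognostic covariates would be kept more often.
- A reader might extend the figures to every arm test in Aims 2 and 3. The pooled analysis of both phases has surgeons changing status between phases, so status varies within surgeon and the degrees of freedom above do not carry over. The Aim 3 analyses of who uses the support, and how much, concern patient-level use.

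It is also fair to say that the design survives the correction: at 40 × 100, a t reference still gives more than 80% power.

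**Conclusion.** The point holds as a gap in specification with a modest, conditional cost. Under maximum likelihood with z, the two-sided error for a continuous outcome in the parallel arm comparison is about 6.5% at 36-40 surgeons with no surgeon-level covariates, about 7% with two, and 8-9% only with about five. With the 54 surgeons that section 13 still gives for Aim 3, it is 6.0-7.4%; that count must be reconciled with the 36-40 in section 4.

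These figures assume surgeons are independent clusters, normal outcomes, an intraclass correlation of 0.02 and two-sided testing. The table assumes equal cluster sizes; the simulation relaxed this. The responder outcome was not simulated. Sections 8 and 11 say that offices are randomised, and section 7 gives 20-30 offices. If offices are the independent unit, the same formula gives 6.9-7.9% with no covariates and 10.0-13.8% with five.

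**What to change.** In the overview, Aim 2 and Aim 3 paragraphs of section 13:

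1. For continuous outcomes, fit the clustered model by REML and test the arm with Kenward-Roger or Satterthwaite degrees of freedom, based on the clusters actually randomised. Take confidence intervals from the same reference.
2. For the responder outcome (meaningful pain relief), use a cluster-level t-test or a permutation test over the randomised units.
3. State one number of surgeons for Aim 3.

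No cap on surgeon-level covariates is needed for this defect, because the degrees of freedom account for them.

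**Cost.** The change is to wording and uses standard software; no extra patients are needed to hold the level. Relative to ML with z, intervals are about 6-10% wider with zero to two surgeon-level terms and up to 16% wider with five. At 40 × 100, power at 0.16 SD is 81.5% with the t reference, against 83.4% by the z formula, and 81.2% with five surgeon-level parameters. At the revised 3,000 patients (40 × 75), it is 77.4% against 79.5%. That shortfall below 80% comes mainly from the smaller patient total, since it is already present with z.
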